5.2 Study Schedule / Duration

Each subject's participation in the study will be comprised of 5 scheduled office visits over approximately 12 months. The entire study is expected to be completed within approximately 24 months from approval of the study protocol and the study device.

5.3 Inclusion Criteria

1. Subject is age 7 to 15 at time of screening
2. Subject has been diagnosed with type 1 diabetes mellitus and must have been diagnosed for at least one year prior to screening
3. Subject is currently transitioning from pump therapy, with or without continued glucose monitoring (CGM), to the 530G insulin pump system.
4. Subject is willing to perform greater than or equal to 4 finger stick blood glucose measurements daily
5. Subject is willing to perform required sensor calibrations
6. Subject is willing to wear the system (Pump, glucose sensors, meter) continuously throughout the study
7. Subject is willing to upload data every 21 days from the study pump
8. Subject must have Internet access and access to a computer system that meets the requirements for uploading the pumps. This may include use of family or friend's computer system with Internet access.
9. Subject is using either Humalog or Novolog at time of Screening and plans to use either of those insulins throughout the study

5.4 Exclusion Criteria

1. Subject is actively participating in an investigational study (drug or device) wherein he/she is receiving treatment from an investigational study drug or investigational study device.
2. Women of child-bearing potential who have a positive pregnancy test at screening or plan to become pregnant during the course of the study
3. Subject is being treated for hyperthyroidism at time of screening
4. Subject has an abnormality ($>1.8\text{mg/dL}$) in creatinine at time of screening visit
5. Subject has an abnormality (out of reference range) in thyroid-stimulating hormone (TSH) at time of screening visit
 - If TSH is out of range, Free T3 and Free T4 will be tested
 - Subject may be included with TSH out of range as long as Free T3 and Free T4 are in normal reference range.
6. Subject has taken any oral, injectable, or IV steroids within 8 weeks from time of screening visit, or plans to take any oral, injectable, or IV steroids during the course of the study
7. Subject is currently abusing illicit drugs
8. Subject is currently abusing prescription drugs
9. Subject is currently abusing alcohol
10. Subject is using pramlintide (Symlin) at time of screening
11. Subject has a sickle cell disease, hemoglobinopathy; or has received red blood cell transfusion or erythropoietin within 3 months prior to time of screening
12. Subject plans to receive red blood cell transfusion or erythropoietin over the course of study participation
13. Subject diagnosed with current eating disorder such as anorexia or bulimia
14. Subject has been diagnosed with chronic kidney disease that results in chronic anemia
15. Subject is on dialysis
16. Subject is already on a 530G system with CGM for 8 days or more.

6. Statistical Methods and Data Analysis

6.1. Sample Size Calculation

6.1.1 Sample Size for Primary Endpoint

The overall mean change in A1C from baseline to the end of study will be estimated and compared by a non-inferiority test with an A1C margin of 0.4%

and a significance level of 0.025 (one-sided). The null hypothesis will be rejected if the one-sided 97.5% upper confidence limit of the mean change in A1C is less than 0.4%.

The hypothesis is mathematically expressed as:

$H_0: \mu \geq 0.4\%$

$H_a: \mu < 0.4\%$

Where 0.4% is the pre-specified non-inferiority margin, μ is the mean of change in A1C (%).

Assuming the mean of change in A1C from baseline to the 12-month follow-up visit is zero, the standard deviation of change in A1C is 1%, SAS power and sample size calculator shows that a total of 100 subjects will provide over 95% power to detect the non-inferiority with a margin of 0.4% and with one-sided type I error of 0.025.

6.1.2 Overall Consideration

The above calculations suggest a sample size of 100 subjects who complete the study. For the drop-out rate, a conservative estimate of 20% is adopted (based on STAR3, IDE G060159, the percentage of subjects not completing study in the SAP group is 9.3%); assume 65% of subjects would wear the system most of the time. Then a total of 193 subjects needs to be recruited. In general, a number of 200 will be eligible to participate in the study, with up to 300 subjects enrolled.

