3.1. Study Objective

The study objective is to demonstrate that home use of Threshold Suspend (TS) is not associated with glycemic deterioration in pediatric patients with type 1 diabetes, as measured by change in A1C.

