6.2.3 Efficacy Population

The primary efficacy analysis will be performed on the CC population.

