10.6 Minimizing subject withdrawal

It may be reasonable to expect that subjects will not consistently comply with study requirements during the study. In this study, continuous sensor wear is a key component in the collection of TS safety data. For this reason, the strategy will be to select investigational centers that have the experience and expertise to manage subjects for an extended period of time in the context of a clinical study. Furthermore, as a means of providing encouragement to study subjects, the following will be implemented:

Subjects will be provided devices and supplies (e.g., glucose sensors, meter strips, ketone strips) that need replenishing free of charge at every study visit.

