14.1.8 Potential risks and mitigations for pediatric subject population

The pediatric subject population has an increased risk for hypoglycemia, including severe hypoglycemia.

Standard mitigations in pediatric subjects include:

- Training of primary caregivers will be conducted in addition to subject training.
- Subject instruction to test BG via finger stick testing 4-6 times a day.
- Subject instruction to adhere to 100% sensor wear.
- Subject instruction to use the bolus wizard when determining meal or correction bolus.

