3.1.2.1.2 Overall Consideration

The above calculations suggest a sample size of 100 subjects who complete the study. For the drop-out rate, a conservative estimate of 20% is adopted (based on STAR3, IDE G060159, the percentage of subjects not completing study in the SAP group is 9.3%); assume 65% of subjects would wear the system most of the time. Then a total of 193 subjects needs to be recruited. In general, a number of 200 will be eligible to participate in the study, with up to 300 subjects enrolled

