3.1.2.2 Analysis Datasets, if applicable

Intention to Treat (ITT) Population

The Intention to Treat (ITT) population will include all enrolled subjects.

Completed Case (CC) Population

The Completed Cases (CC) population is all subjects who complete the trial.

Efficacy Population

The primary analysis will be performed on the CC population. Sensitivity analysis will be performed in the ITT population with multiple imputations.

Safety Population

The safety population will be the ITT population (include all enrolled subjects).

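### Does the 65% wear factor behind the recruitment target of 193 call for a wear-based analysis or a different target?

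*Protocol*

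**What the plan says.** Protocol 6.1.1 tests whether the mean 12-month change in A1C is below 0.4%, at one-sided 0.025, assuming a true change of zero and an SD of 1%. It states that 100 subjects give over 95% power. Protocol 6.1.2 describes these 100 as completers: "The above calculations suggest a sample size of 100 subjects who complete the study". It then allows for 20% dropout and for incomplete wear: "assume 65% of subjects would wear the system most of the time. Then a total of 193 subjects needs to be recruited". It plans for 200 eligible subjects with up to 300 enrolled. SAP 3.1.2.1.2 repeats the wear allowance: "assume 65% of subjects would wear the system most of the time".

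The analysis sets are defined without reference to wear. Protocol 6.2.3 says "The primary efficacy analysis will be performed on the CC population", and SAP 3.1.2.2 says "The Completed Cases (CC) population is all subjects who complete the trial". The ITT and safety sets are everyone enrolled, and the one readable sensitivity analysis is ITT with multiple imputation.

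The objective (Protocol 3.1) is to show that "home use of Threshold Suspend (TS) is not associated with glycemic deterioration in pediatric patients with type 1 diabetes".

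**The concern.** An inflation factor normally stands for subjects who will not count in the analysis. A 65% wear factor therefore suggests that low wearers are to be set aside, but the primary set keeps them. Either the target is larger than the primary test needs, or an analysis of wearers was intended and is not visible. The wear phrase also has no numerical threshold.

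Interpretation would be at stake. Threshold Suspend works only with continuous glucose monitoring (Protocol 2.1.1). Protocol 14.1.8 lists "Subject instruction to adhere to 100% sensor wear", while Protocol 10.6 concedes "It may be reasonable to expect that subjects will not consistently comply with study requirements during the study". On the plan's own figure, 35% would not wear the system for the greater part of the study. In a single-arm non-inferiority test, low exposure could pull the average towards no change, which is the direction of success.

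**Working it through.** **Inputs (Protocol 6.1.1 and 6.1.2; the same in the SAP).** Margin 0.4, SD 1, true change 0, one-sided alpha 0.025, 100 completers, dropout 20%, wear 65%, 200 eligible.

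**1. Reproduce the target.**
- Both factors: 100/0.80/0.65 = 192.3, rounded up to 193. This matches the plan.
- Dropout only: 100/0.80 = 125.
- Wear only: 100/0.65 = 153.8, rounded up to 154.

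The wear factor is needed to reach 193 and accounts for 193 - 125 = 68 recruits.

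**2. Power of the all-completer test.** A one-sample t-test stands in for the planned mixed model. Power = P(T > t(0.975, n-1)), where T is noncentral t with n-1 degrees of freedom and noncentrality 0.4 x sqrt(n)/1.

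| Recruits | Completers at 80% | Noncentrality | Power |
|---|---|---|---|
| 125 | 100 | 4.00 | 97.7% |
| 193 | 193 x 0.80 = 154 | 4.96 | 99.85% |
| 200 | 200 x 0.80 = 160 | 5.06 | 99.89% |

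The claim of over 95% holds at 100 completers; 95% alone needs 84. The factor can only raise power for the stated test, and it plays no part in the type I error.

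**3. Could the study be smaller without the factor?** Not down to 125. Protocol 5.1 sets minimums of 80 boys and 80 girls (80 + 80 = 160) and 50 in each of three A1C cohorts (3 x 50 = 150). The plan for 200 eligible subjects covers both.

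**4. Does pooling low wearers make the test wrong?** Assume, as an illustration not taken from the documents, that 65% of completers are wearers with a true rise of exactly 0.4.
- Low wearers with no rise: the pooled mean is 0.65 x 0.4 = 0.26. With 160 completers and a within-group SD of 1, the test passes about 41% of the time.
- Low wearers rising by 0.6: the pooled mean is 0.65 x 0.4 + 0.35 x 0.6 = 0.47, and the test passes about 0.2% of the time.

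In the first case the overall mean really is below 0.4, so a pass is a correct decision on the stated hypothesis. In the second it is above 0.4, and the test almost always fails, as it should. The direction depends entirely on what is assumed for low wearers.

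**5. Would a split by wear settle the question?** With 160 completers, 160 x 0.65 = 104 are wearers and 56 are not. If instead every dropout is a low wearer, 200 x 0.65 = 130 are wearers and 30 are not. The standard error of the difference (SD 1) is sqrt(1/104 + 1/56) = 0.166 or sqrt(1/130 + 1/30) = 0.203. The 95% half-widths are about 0.32 and 0.40. Power to detect a difference as large as 0.4 is about 67% and 51%.

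**The case for a change.** The strongest case for a change is that the trial makes a claim about Threshold Suspend, that Protocol 10.6 treats continuous sensor wear as central to the safety data on it, and that the plan itself expects a third of subjects to fall short. Recruitment at 200 already pays for an analysis of about 104 wearers, with 98.1% power against the 0.4 margin. The pump uploads are collected anyway. Naming that analysis and fixing a threshold before database lock would cost a few sentences and one more model run.

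Part of this stands. The sample-size paragraph does not say what the 65% is for, and the wear phrase has no cut-off.

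The demand for an added analysis does not follow, for three reasons. First, SAP numbering runs from 3.1.5.1 to 3.1.5.4 with withheld text between, and Protocol 6.5 breaks off after its cohort list. A supportive wear analysis would naturally sit there and cannot be counted as absent. Second, wear is not exposure to the feature. The Protocol's terminology separates the feature being on from its being off, and the readable text does not say that uploads record this status. Third, a wearer subset is selected on behaviour after baseline, with no control arm. Even a clear difference could reflect who adheres rather than what the feature does, and step 5 shows that the difference would often be unclear.

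**Conclusion.** No change to the plan is needed. The 65% works as a conservative recruitment allowance: 68 of the 193 recruits, lifting power from 97.7% to about 99.9% for the test as defined. Type I error and the primary conclusion are unaffected. An all-completer mean suits an objective about home use, where imperfect wear is part of what is being observed. A sentence saying whether the 65% is a margin or serves a named analysis would help readers, but it is optional and alters no result.

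The power figures rest on the plan's SD of 1%, true change of zero and 20% dropout, with a one-sample t-test in place of the mixed model. The conclusion that nothing is missing is limited to the readable text, since parts of SAP 3.1.5 are withheld.

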6.2 Study Populations

6.2.1. Intention to Treat (ITT) Population

The Intention to Treat (ITT) population will include all enrolled subjects.

6.2.2 Completed Case (CC) Population

The Completed Cases (CC) population is all subjects who complete the trial.

6.2.3 Efficacy Population

The primary efficacy analysis will be performed on the CC population.

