6.3 Analysis of Primary Endpoint

6.3.1 Primary Efficacy Analysis

A mixed effects model be used to produce the estimate and confidence interval of the overall mean change in A1C while accounting for inter-site variability. The 97.5% upper confidence interval of A1C will be calculated and compared to the 0.4% non-inferiority margin. As for endpoint analysis, the proposed mixed effects model using all A1C measurements has more power than the model only using Change in A1C from baseline to one-year visit.

$$Y_{ij} = X_{ij}\beta + B_i + B_{ij} + \epsilon_{ij}$$

where

$\mathbf{I}_j = (I_{j1}, \dots, I_{jT})'$ is the A1C measurement vector for the jth subject in the ith site;

$$\begin{bmatrix} 1 & 0 & 0 & 0 \\ 1 & 1 & 0 & 0 \\ \vdots & \vdots & \vdots & \vdots \\ 1 & 0 & 1 & 0 \\ 1 & 0 & 0 & 1 \end{bmatrix}$$

$\mathbf{C}_j = (C_{j1}, \dots, C_{jT})'$ is a the covariate vector for the jth subject in the ith site;

$$\begin{bmatrix} \beta_0 \\ \beta_1 \\ \beta_2 \\ \vdots \\ \beta_4 \end{bmatrix}$$

[figure not shown]
$\beta = \begin{bmatrix} \beta_0 \\ \beta_1 \\ \beta_2 \\ \vdots \\ \beta_4 \end{bmatrix}$ is the coefficient vector, β_0 estimate the mean A1C at baseline, β_1 estimate the mean change of A1C from baseline to one-year visit;

$\mathbf{B}_i = (b_{i1}, \dots, b_{iT})'$ is the random effect vector for the ith site;

$\mathbf{B}_j = (b_{j1}, \dots, b_{jT})'$ is the random effect vector for the jth subject in the ith site;

$\mathbf{e}_j = (e_{j1}, \dots, e_{jT})'$ is the random error term;

"The mean of baseline A1C measurement is estimated by β_0 , mean of 3-month A1C measurement estimated by $\beta_0 + \beta_1$, ..., mean of 12-month A1C measurement estimated by $\beta_0 + \beta_1 + \dots + \beta_4$, i.e., β_1 estimate the mean change of A1C from baseline to one-year visit; the 97.5% upper confidence interval of β_1 will be calculated and compared the 0.4% non-inferiority margin."

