10.1 Visit 1 - Day 0: Consent and Screening

General

Eligibility:

This study is open to all individuals who meet the eligibility criteria. Subjects will be considered enrolled after they have signed the Informed Consent form. The Investigational Center will be responsible for making adequate source documentation available to the sponsor to verify subject eligibility.

General

Standard Care:

It is expected that subjects will continue to undergo their routine diabetes care as per clinic standard. During routine quarterly visits data collection for the study will be obtained by the designated staff.

General

Investigational Center staff will:

- Obtain informed consent/Accent from subject/parent/caregiver
 - Subjects 7-15 years should provide assent in addition to Informed Consent from parent/caregiver
- Assess eligibility of subjects to participate in the study
- Collect demographic information and baseline characteristics, including age, gender, race, ethnicity and medical diagnosis, duration of diabetes (Screening eCRF).
- Record concomitant medications on appropriate CRF
- Obtain blood sample(s) to complete required screening A1C test, if all eligibility criteria (excluding those involving blood test results) are met:
Note: All collected blood specimens will be sent to and tested by a NGSP certified Central Laboratory. A1C testing must follow National Glycohemoglobin Standardization Program (NGSP) standards. This A1C will be used for data analysis.
- Obtain blood samples to complete required screening tests, i.e. TSH (also T3, T4 if TSH is abnormal), Creatinine
- Perform screening labs including urine or serum pregnancy test
- Subjects may be rescreened up to a maximum of two times if they do not meet inclusion/exclusion criteria at the time of their original screening
- Register subjects in CareLink Clinical (see Investigator/Coordinator binder for details) and **upload insulin pump**
- Disburse devices and supplies (e.g., pump, transmitter, glucose sensors, Bayer meter, meter strips, ketone strips) to each study subject
- Administer the following questionnaires:
 - Hypoglycemia awareness questionnaire
 - Score of 4 or more is impaired awareness. It means that subjects with this score will be assigned to the impaired hypoglycemic awareness cohort.
 - Score of 3 or less is aware. It means that subjects with this score will be assigned to the intact hypoglycemic awareness cohort.
 - EQ-5D Youth
 - Hypoglycemia Fear Scale (HFS) – Child/Teen

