10.7 Subject Withdrawal

Subject/parent/caregiver may choose to withdraw from the study at any time by notifying Investigational Center staff of their intent.

If a subject chooses to end his or her study participation or if a subject is removed from the study at the Investigator's discretion, the reason for termination must be documented both in source documents and on the appropriate eCRF.

A subject will be withdrawn from the study by the investigator if:

- In the opinion of the Investigator, the subject's health or safety would be compromised by continuing in the study
- In the opinion of the Investigator, it is in the subject's best interest to discontinue participation in the study
- During the course of the study, subject has 2 episodes of DKA (see definition in section 14.4)
- During the course of the study, subject experiences 2 episodes of severe hypoglycemia
- During the course of the study, subject begins abusing illicit drugs.
- During the course of the study subject begins abusing prescription drugs.
- During the course of the study subject begins abusing alcohol.
- During the course of the study subject begins using pramlintide (Symlin).
- During the course of the study, subject receives red blood cell transfusion or erythropoietin.
- During the course of the study, subject takes any oral, injectable, or IV steroids.

Documentation of the reason(s) leading to subject withdrawal will be kept in the subject's source file.

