3.1.3 Disposition

3.1.3.1 Subject Disposition

The number of subjects enrolled in the study will be presented. The reasons for discontinuing prior to study completion will be summarized.

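### The pass/fail non-inferiority test is run on completers only, although some withdrawals are tied to glycemic events; the bias can go either way, and the power claimed for the model is essentially absent in that set

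*Protocol*

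**What the plan says.** Protocol 6.2.3 and SAP 3.1.2.2 both place the deciding analysis on the completed-case (CC) set. The protocol says "The primary efficacy analysis will be performed on the CC population" and defines the set in 6.2.2: "The Completed Cases (CC) population is all subjects who complete the trial". The SAP adds one further analysis: "The primary analysis will be performed on the CC population. Sensitivity analysis will be performed in the ITT population with multiple imputations". The ITT set is everyone enrolled, and Protocol 10.1 fixes that moment: "Subjects will be considered enrolled after they have signed the Informed Consent form".

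Protocol 10.7 lists reasons for which the investigator must withdraw a subject. Two are glycemic: "During the course of the study, subject has 2 episodes of DKA" and "During the course of the study, subject experiences 2 episodes of severe hypoglycemia". Steroid use and the investigator's judgement on health or safety are also listed, and families may leave at any time.

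Protocol 6.3.1 and SAP 3.1.5.1 justify the model by stating that "the proposed mixed effects model using all A1C measurements has more power than the model only using Change in A1C" from baseline to one year. On drop-out, SAP 3.1.3.1 says: "The reasons for discontinuing prior to study completion will be summarized".

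**The concern.** The objective in Protocol 3.1 concerns home use of Threshold Suspend in pediatric patients, not only in those who finish a year. In a one-arm comparison with a fixed margin, any difference between leavers and completers enters the estimate in full. Leavers' A1C values at 3, 6 and 9 months are collected but play no part in the decision.

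If leavers do worse than completers, the test can pass although the mean over all treated subjects sits at the margin. If they do better, it can fail wrongly. The direction cannot be read from the documents. Subjects withdrawn for severe hypoglycemia may well have low A1C, while those withdrawn for DKA or steroid use may have high A1C.

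A second, minor point follows. The advantage claimed for using all A1C measurements comes from subjects with partial follow-up, and the CC set removes them.

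**Working it through.** **Inputs from the documents.** Margin 0.4%, one-sided alpha 0.025, SD of change 1%, assumed mean change 0, and 100 completers (Protocol 6.1.1). Drop-out 20%, reference non-completion 9.3%, 65% wear, 193 recruited, 200 eligible, up to 300 enrolled (Protocol 6.1.2).

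**The plan's own figures.** With n = 100, SE = 1/√100 = 0.10 and the noncentrality is 0.4/0.10 = 4. The noncentral t gives 97.7% power, consistent with the stated figure of over 95%. The inflation is 100/(0.80 × 0.65) = 192.3, rounded up to 193. Both reproduce. The CC definition carries no wear condition, so 200 eligible at 20% drop-out leave 160 completers and 99.9% power. Power is not the problem.

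**Size of the selection effect.** Let d be the drop-out fraction and gap = leavers' mean change minus completers' mean change. The gap is assumed; no document gives it. Then

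all-subject mean = completer mean + d × gap.

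Set the all-subject mean at 0.4, so the completer mean is 0.4 − d × gap. The probability of passing comes from the noncentral t with n = 160 (d = 0.20) or n = 181 (d = 0.093; 200 × 0.907 = 181.4). The site effect is ignored.

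| Gap | d = 20% | d = 9.3% |
|---|---|---|
| −0.5 | 0.06% | 0.5% |
| −0.25 | 0.5% | 1.2% |
| 0 | 2.5% | 2.5% |
| +0.25 | 9.2% | 5.0% |
| +0.5 | 24.1% | 9.1% |
| +1.0 | 71.0% | 23.7% |

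With the plan's 100 completers at 20% drop-out, gaps of +0.5 and +1.0 give 16.6% and 50.8%. If only 1–2% of subjects differ, by one point (n = 160), the rate is 3.3–4.4% when they are worse and 1.9–1.4% when they are better. In the other direction, with a true all-subject mean of 0, 160 completers and leavers 0.5 or 1.0 better, the pass rate falls from 99.9% to 96.5% or 71.0%.

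**How large a gap would overturn a pass.** Gap = (0.4 − completer upper limit)/d. The half-width of the limit is 1.975 × 0.0791 = 0.156 at n = 160 and 1.973 × 0.0743 = 0.147 at n = 181.

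| Completer mean | d = 20% | d = 9.3% |
|---|---|---|
| 0 | (0.4 − 0.156)/0.20 = 1.22 | (0.4 − 0.147)/0.093 = 2.72 |
| +0.1 | 0.72 | 1.65 |
| +0.2 | 0.22 | 0.57 |

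**What an all-data model changes.** Simulations used 5,000 trials of 200 subjects, with assumed correlations with baseline of 0.85, 0.75, 0.68 and 0.60 over the four follow-up visits, and 20% drop-out depending on A1C change already observed.

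| Resulting gap | CC passes | All-data model |
|---|---|---|
| −0.41 | 0.1% | 2.3–2.6% in every setting |
| +0.21 | 7.7% | as above |
| +0.43 | 20.0% | as above |
| +0.76 | 52.8% | as above |

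If a gap of +0.5 is not fully visible before exit, the all-data model (SE 0.0755) is still biased. Its expected estimate is 0.331 if the gap builds linearly and 0.300 if it appears after the last visit. The pass probabilities are Φ(0.069/0.0755 − 1.96), about 15%, and Φ(0.100/0.0755 − 1.96), about 26%. Adding delta 0.5 to leavers' month-12 values moves the estimates by 0.20 × 0.5 = 0.10, to 0.431 and 0.400, and the rates to 0.9% and 2.5%.

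**The power statement.** Generalised least squares was applied with the SAP's five-visit design matrix, a separate mean per visit and a full within-subject covariance. In 160 completers the month-12 coefficient has SE 0.0791 = 1/√160, identical to the paired change score, under each covariance tried (baseline to month-12 correlation 0.60, 0.65, 0.70). Adding 40 leavers spread over one to four observed visits gives 0.0755–0.0760. The gain therefore exists only when non-completers are included.

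**The case against.** The strongest reply is that the documented mechanism may touch few subjects. The explicit glycemic triggers are two DKA or two severe hypoglycemia episodes, no frequency is given, and the 1–2% case moves the error rate only slightly. The 24.1% and 71.0% figures need all leavers together to average 0.5 or 1.0 points worse, which nothing in the documents supports. The plan also calls 20% conservative beside a 9.3% reference, and at 9.3% with a completer mean of 0 it would take leavers about 2.7 points worse to overturn a pass. All of this stands. It limits the likely size but does not make completers the right deciding set.

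Second, the SAP already plans ITT multiple imputation. That deserves credit, but it is a sensitivity analysis that does not decide the result. Its set includes everyone who signed consent, so up to 300 − 200 = 100 people may never have been eligible or worn the pump. Text near the primary analysis in the SAP is redacted, so further missing-data analyses may exist there and cannot be judged.

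Third, the all-data model is no cure. If deterioration follows the last visit it falsely passes about 26% of the time, no better than the 24.1% for completers. The delta figures take delta equal to the assumed true gap, so they show what the tool can do and do not estimate what it will find. This is why a range of deltas is needed.

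Fourth, the design section speaks of change while subjects wear the pump, and the sample size counts completers. A completer target could be argued from this, but the stated objective is not so restricted.

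**Conclusion.** The concern holds and should be fixed. Both documents rest the pass/fail decision on completers, some withdrawals are tied to glycemic events, and no control arm offsets the selection. That the plan does this is certain. How much it matters depends on an assumed gap whose sign is unknown. At 20% drop-out, gaps of ±0.5 turn a nominal 2.5% false-pass rate into 24.1% or 0.06%; at 9.3% drop-out, into 9.1% or 0.5%. If only 1–2% of subjects differ by a point, the effect is small. A completer mean near 0 would be hard to overturn; one near +0.2 would not. These figures assume 200 eligible subjects, SD 1% and no site effect.

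The power statement is essentially untrue for completers who have baseline and month-12 values. Completers without a month-12 value, whom the CC definition does not exclude, would allow a small gain. It has no practical effect on power at this sample size and needs only a wording correction.

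**What to change.** 1. Make the primary set all eligible subjects who started the study pump and have a baseline A1C. Fit the mixed model to every available A1C, with an unstructured within-subject covariance, and test the baseline to month-12 contrast (β_4 in the SAP's design matrix).
2. Keep the CC analysis as supportive.
3. Run the planned multiple imputation on this same set instead of on all consented subjects.
4. Add a delta-adjusted (tipping-point) analysis with a prespecified range of deltas, reported next to the primary result. Withdrawal reasons are already recorded, so delta can be applied by reason.
5. Correct or delete the sentence on power in both documents.

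The cost is wording in the protocol and SAP and a little more programming, with no new data or visits. The estimate may turn out less favourable. At a true mean change of 0, power remains above 99% for the all-data model and about 98% for its delta 0.5 version: Φ(0.300/0.0755 − 1.96) = 97.8%.
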